12.2 Location: 1 nodal basin vs. >1 nodal basin

12.3 Baseline tissue PD-L1 staining: None versus low versus high

12.4 BRAF mutation status: wild type or mutated

## **13.0 Treatment/Follow-up Decision at Evaluation of Patient**

### **13.1 Neoadjuvant phase**

13.11 Patients who have not had progression of disease or intolerable toxicity may continue on study per protocol.

13.12 Patients who have not had disease progression but develop intolerable toxicity during neoadjuvant treatment may be eligible for retreatment at a lower dose ([Section 8.0](#)) or proceed to surgery.

13.13 Patients who progress during neoadjuvant treatment and are still surgical candidate may proceed to surgery.

13.14 Patients who progress during neoadjuvant treatment and are no longer a surgical candidate will complete on-study, neoadjuvant treatment, and end of protocol treatment form. Survival follow-up is required. Subsequent treatment is at the discretion of the patient's medical team.

13.15 Patients who are no longer a surgical candidate after discontinuation of neoadjuvant treatment for reasons other than disease progression will complete on-study, neoadjuvant treatment, and end of protocol treatment form. Survival follow-up is required. Subsequent treatment is at the discretion of the patient's medical team.

13.16 Patients who discontinue neoadjuvant treatment and are refusing all remaining protocol treatment (that is, surgery and adjuvant treatment) will complete on-

study, neoadjuvant treatment, and end of protocol treatment form. Survival follow-up is required. Subsequent treatment is at the discretion of the patient's medical team.

- 13.17 Patients who discontinue neoadjuvant treatment due to other medical conditions will complete on-study, neoadjuvant treatment, and end of protocol treatment form. Survival follow-up is required. Subsequent treatment is at the discretion of the patient's medical team.

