##### 14.42 Soluble PD-L1 assays

In addition to being expressed as a cell surface ligand in the tumor microenvironment, PD-L1/B7-H1 can be secreted and measured in plasma; soluble PD-L1 (sPD-L1) is associated with prognosis in several tumor types (Frigola 2011). Moreover, in contrast to intratumoral PD-L1, sPD-L1 is associated with a lack of responsiveness to anti-PD-1 therapy in melanoma (Dronca RS et al 2017, and manuscript in preparation).

[figure not shown]
Using our previously published enzyme-linked immunosorbent assay (ELISA) for sPD-L1 (Frigola 2011), we will quantitate sPD-L1 concentrations in patient plasma prior to initiation of neoadjuvant therapy and after neoadjuvant therapy. We will correlate baseline sPD-L1 concentration and the change in PD-L1 concentration from baseline to post-neoadjuvant therapy with response at the time of surgery (pCR versus no pCR) and with RFS.

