#### 16.2 Correlative endpoints

##### 16.21 Pretreatment sPD-L1, pretreatment tumor PD-L1, and pretreatment intracellular Bim in tumor-related T cells

To gather preliminary data as to whether the RFS of patients with stage III melanoma receiving neoadjuvant vem/cobi/atezo or atezo, followed by surgery and adjuvant atezo differs with respect to either pretreatment sPD-L1 or pretreatment intracellular Bim in tumor-related T cells, stratified Cox modeling will be conducted with patient cohort as the strata to obtain a point and interval estimate of the hazard of recurrence among those with biomarker levels thought to be delirious relative to the hazard of recurrence among those with biomarker levels thought not to be delirious.

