## 17.4 Background and methodology

### 17.41 PD-L1 IHC

Validated in lung cancer as a biomarker of response, PD-L1 expression assessed by IHC in tumor tissue has been reported to correlate with treatment response in a recently published melanoma adjuvant therapy studies (Weber 2017). However, validation of cut-points and the best approach to evaluate heterogeneous staining remains to be determined (Scognamiglio 2016). We will test biopsy samples from the time of diagnosis and samples tested at the time of operation to evaluate the association, if any, to neoadjuvant therapy response and other endpoints. FFPE sections will be stained using a commercially available FDA-approved kit and percent membrane staining assessed qualitatively.

Immunohistochemistry for PD-L1 will be performed using the FDA-approved kit VENTANA PD-L1 (SP263) Assay which is a qualitative immunohistochemical assay using rabbit monoclonal anti-PD-L1 clone SP263 intended for use in the assessment of the PD-L1 protein in formalin-fixed, paraffin-embedded (FFPE) tissue.

PD-L1 status will be determined by the percentage of tumor cells with any membrane staining above background or by the percentage of tumor-associated immune cells with staining (IC+) at any intensity above background. The percent of tumor area occupied by any tumor-associated immune cells (Immune Cells Present, ICP) is used to determine IC+, which is the percent area of ICP exhibiting PD-L1 positive immune cell staining. Staining will be assessed semi-quantitatively based on percent membrane staining.

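### Section 16.21 relates pretreatment sPD-L1 and Bim to RFS only through a two-group split at an unstated level, although both markers are continuous

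*Combined protocol and SAP*

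**What the plan says.** Section 16.21 states an exploratory aim: "To gather preliminary data as to whether the RFS of patients with stage III melanoma" on the trial regimens varies with two markers, that is, whether it "differs with respect to either pretreatment sPD-L1 or pretreatment intracellular Bim in tumor-related T cells". The method is that "stratified Cox modeling will be conducted with patient cohort as the strata". The result is an estimate, with an interval, of the recurrence hazard in patients whose levels are believed harmful, taken "relative to the hazard of recurrence among those with biomarker levels thought not to be delirious". That is a contrast between two groups. The section gives no threshold, no rule such as a median split, no source, no test and no confidence level. Tumor PD-L1 is in the section heading but not in the model sentence.

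The markers themselves are quantities. Under Section 14.42, "we will quantitate sPD-L1 concentrations in patient plasma prior to initiation of neoadjuvant therapy" by ELISA. Section 14.41 measures the frequency of Bim-positive tumor-related T cells. Neither section names a threshold. Both say that baseline values and changes will be correlated with RFS and pCR, without naming a method.

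For tumor PD-L1, Section 12.3 lists "Baseline tissue PD-L1 staining: None versus low versus high" without numeric limits, and Section 17.41 says that "validation of cut-points and the best approach to evaluate heterogeneous staining remains to be determined".

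**The concern.** Two analysts working from Section 16.21 could place the cut differently and report different hazard ratios from the same data. Even a well-placed cut discards the ordering of patients within each group, and a trial of this size has few events to spare. Leaving the cut open also leaves room to choose it after the RFS data are seen, in which case the reported interval would no longer mean what it says.

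At stake are the pretreatment parts of objectives 2.31 (sPD-L1) and 2.32 (Bim). The on-treatment and later time points in those objectives are not covered by Section 16.21. Objective 2.34 (tumor PD-L1) has no explicit RFS model at all.

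**Working it through.** The plan states no power, event count or effect size for this model, so there is no figure of its own to reproduce.

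**Inputs from the documents.** Arms A and B have 15 patients each (schema), and Arm C has 32 starting treatment (Section 16.1112). Section 16.22 extends the same correlative studies to Arm C, so the pooled total is 15 + 15 + 32 = 62. RFS is analyzed only in patients who began adjuvant treatment (Section 16.12), so 30 and 62 are upper limits.

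**Assumptions.** Event fractions of 30% or 50% give D = 9 or 15 events of 30, and 19 or 31 of 62. The effect is log-linear, with a hazard ratio (HR) of 1.5 or 2.0 per SD of a normal marker. One further scenario has 58 patients and a hazard of 0.0118 per month over 36 months: 1 − exp(−0.4248) = 0.346, and 58 × 0.346 ≈ 20 events, with 3-year RFS of 65%.

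**1. Information kept by a split at quantile p.** Efficiency = φ(z_p)² / [p(1 − p)].
- Median: 0.3989² / 0.25 = 0.637, so 1/0.637 = 1.57 times the events are needed for equal power.
- 25/75 split: 0.54 (1.86 times the events).
- 20/80 split: 0.49 (2.04 times the events).

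**2. Power at two-sided 5%.** Power = Φ(√(D × eff) × ln HR − 1.96), with eff = 1 for the continuous marker.

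| Events | HR per SD | Continuous | Median split |
|---|---|---|---|
| 9 | 1.5 | 23% | 16% |
| 15 | 1.5 | 35% | 24% |
| 19 | 1.5 | 42% | 29% |
| 31 | 1.5 | 62% | 44% |
| 9 | 2.0 | 55% | 38% |
| 15 | 2.0 | 77% | 57% |
| 19 | 2.0 | 86% | 67% |
| 31 | 2.0 | 97% | 87% |

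The loss runs from 7 to 19 points. Simulation of the stratified Cox score test (3,000 runs per setting) gives lower absolute power in most settings and gaps of 5 to 21 points. Examples are 42% against 27% (30 patients, 30% events, HR 2.0) and 91% against 74% (62 patients, 50% events, HR 2.0).

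**3. The 20-event scenario at two-sided 10%, log-HR 0.5 per SD.**
- Continuous: Φ(√20 × 0.5 − 1.645) = Φ(0.59) = 72%.
- Median split: Φ(√(20 × 0.637) × 0.5 − 1.645) = Φ(0.14) = 56%.
- Simulation: 72% against 52% unstratified, and 69% against 52% stratified by cohort.

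**4. Width of the two-group interval.** The standard error of the log-HR is 1/√(D p(1 − p)). For a 50/50 split, 95% limits are the HR divided and multiplied by 3.7 (9 events) to 2.0 (31 events). For a 20/80 split the factor is 5.1 to 2.4.

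**5. If the cut were chosen on the data.** With no true association, keeping the best of 13 cuts between the 20th and 80th percentiles gives 42% false positives at a nominal 10% (43% stratified). Searching every value in the inner 60% or 80% gives 46–61% at a nominal 10%, and 28–41% at a nominal 5%, per biomarker. A continuous marker or a pre-set median cut stays near nominal: 5–6% at 5%, and 10–11% at 10%.

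**6. The reverse case.** Suppose the true effect is a step (HR 2.7, 21 events, two-sided 10%) and the cut falls exactly on it. The split gives Φ(√(21 × 0.25) × ln 2.7 − 1.645) = Φ(0.63) = 74%. The continuous model gives Φ(√(21 × 0.25 × 0.637) × ln 2.7 − 1.645) = Φ(0.17) = 57%. Simulation gives 72% against 55%. A cohort-stratified simulation with a step at the median gave a smaller gap, 61% against 54%. A sample-median cut that only approximates the true step accounts for a gap of that size.

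**The case against.** The strongest reply is that the plan's wording points to prior belief about which levels are harmful. Sections 14.41 and 14.42 cite the group's own published assays and give expected directions: high Bim with response to anti-PD-1, and high sPD-L1 with lack of response. A cut may exist in those sources. A reader might infer that the cut will be picked from this dataset, but nothing in the documents says so. The inflated error rates are therefore conditional. What stands is that no cut or source is written down, so a search is not excluded.

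The reply can add that 14.41 and 14.42 speak of correlating baseline values with RFS, so a quantitative analysis is not ruled out. That is true, but the only RFS model specified for these markers is the two-group one.

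The power comparison also depends on the shape of the effect. If the truth is a step close to the chosen cut, the split wins by about 7 to 17 points. That objection stands as a limit. A log-linear model is the more cautious default because it does not require the step to be located in advance, but about 20 events will not settle the shape.

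Two further readings go too far. One is that this model also splits tumor PD-L1. The model sentence omits it, and the caution in 17.41 about cut-points concerns tissue staining, not the ELISA or the Bim assay. The other is that a reported 90% interval would lose coverage. Section 16.21 states no level; 90% is the level in 16.12 for RFS, while 16.22 uses 95% for T cell clonality.

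**Conclusion.** The point holds in a limited form. The only specified RFS analysis of pretreatment sPD-L1 and Bim is a two-group contrast at an unstated level. For a normal marker with a log-linear effect, even the best-placed split gives up about 36% of the information (1 − 0.64). The loss in power is 7 to 19 points at two-sided 5% under the stated assumptions, and about 17 to 20 points in the simulated 20-event scenario at two-sided 10%. The event counts and effect sizes are assumptions, not trial figures.

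A reader might conclude that the plan commits to a data-driven cut, or that splitting is always weaker. The documents do not support the first, and a true threshold effect contradicts the second. The analysis is labelled preliminary and aims at estimation, so the practical cost is imprecise and poorly reproducible hazard ratios, not a failed test. No primary endpoint, sample size or stopping rule depends on it. The change is worth making because it is cheap and needs no new data.

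**What to change.** In Section 16.21, state that each biomarker enters the cohort-stratified Cox model as a continuous covariate (log scale for sPD-L1). The hazard ratio per SD, with its interval at a named confidence level, should be the main estimate. Use groups only for Kaplan-Meier display, or as a secondary analysis with the cut and its source fixed before outcomes are examined. Apply the same model to tumor PD-L1 percent staining, so that the heading and the text agree and objective 2.34 has an RFS model. Correct the word that should read deleterious.

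The cost is about one sentence of SAP text. The downside is the log-linearity assumption. A plot can give a rough check, but with so few events it will be weak, and some power would be lost if the true effect is a threshold near the cut that would have been used. The pre-specified secondary split covers that case.

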##### 16.22 Other correlative evaluations

Evaluate associations between molecular features of melanomas and the tumor immune microenvironment in responders (pCR) versus non-responders (non-pCR) with mIHC and RNASeq in patients with stage III melanoma after neoadjuvant vem/cobi/atezo or atezo, followed by surgery and adjuvant atezo. Graphs will be constructed to visually compare and contrast the levels of these biomarkers between those who achieve a pCR and those who did not. Binomial confidence intervals for the difference in two independent proportions or t confidence intervals for the difference in two independent means will be used to gain preliminary insights into the difference in these biomarkers among those who achieve a pCR and those who did not.

Changes in the concentration of circulating tumor DNA during neoadjuvant treatment will be correlated with pCR. Graphs will be constructed to visually compare and contrast the level of tumor DNA between those who achieve a pCR and those who do not.

For evaluation of changes in T cell receptor clonality, the percent change in the clonality after post neoadjuvant therapy from pre-neoadjuvant therapy levels will be determined for the intra-tumoral T cells from the primary lesion and for peripheral blood T cells. A waterfall plot of the percent change will be constructed by pCR status. A two sample Wilcoxon rank sum test will be used to assess whether the percent change in intra-tumoral T cells from the primary lesion or in peripheral blood T cells differ among those who have a pCR and those who do not. Also, the proportion of patients who have a change in intra-tumoral T cell clonality and the proportion of patients who have a change in peripheral blood T cell clonality will be determined. For each of these parameters, a 95% binomial confidence interval for the difference in the parameter between those who have a pCR and those who do not will be constructed. Finally, the ratio of the intra-tumoral T cell clonality in the involved lymph node to the intra-tumoral T cell clonality in the uninvolved lymph node will be determined. This ratio will be summarized descriptively using median and inter-quartile range.

For evaluation of changes in peripheral blood immune cell subsets, we will quantitate the percentage of PBMCs comprising each immune cell type at each time point. The change in each immune cell subset frequency from pre- to post-neoadjuvant therapy, post-neoadjuvant therapy to post-surgery, and post-surgery (pre-adjuvant therapy) to post-adjuvant therapy will be calculated. Pre-treatment immune subset frequencies and changes in frequencies that occur during treatment will be correlated with pCR/near pCR. Graphs will be constructed to visually compare and contrast immune cell subset changes between those who achieve a pCR and those who do not.

We plan to perform the same correlative studies for Arm C of MC1776 as for Arms A and B. These include determining the associations between soluble and tissue PD-L1 with RFS, determining the association between intracellular Bim levels on tumor-associated T cells with RFS, evaluating associations between molecular features of melanoma (assessed by RNA-Seq) and the tumor immune microenvironment (assessed by multiplexed immunofluorescence) with RFS, evaluating changes in cell-free DNA over time and correlating these with clinical outcomes, and evaluating T cell receptor diversity and T cell neoantigen responses in peripheral blood and treated lymph nodes. We also plan to study the host microbiome at serial time points in association with the above as well as local and systemic immunity assays and treatment response.

In addition, to further characterize changes in peripheral blood mononuclear cells (PBMCs), we plan to perform CyTOF analysis of peripheral blood mononuclear cells at multiple time points and correlate changes in PBMC subsets with other biomarkers (as noted above) and with RFS.

We will determine therapeutic response in the index node in the same manner as described for pathologic assessment of the nodal basin in the protocol. We will correlate pathologic response in the index lymph node with pathologic response in the remaining nodes in the entire dissected basin.

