A combined preliminary analysis of four of these trials (exclusive of the one testing interferon) was presented in the summer of 2017 (Menzies 2017). The investigators reported on 58 patients with stage III melanoma who had completed neoadjuvant therapy (18 immunotherapy, 40 targeted therapy) and proceeded to operation. They saw a pCR in 39% to immunotherapy and 55% to targeted therapy. Interestingly, after 10 months median followup, the recurrence rate was three times higher for patients treated with targeted therapy alone (12 of 40, 33%) than for immunotherapy (2 of 18, 11%). Recurrence rates were lower among patients with a pCR (0 of 7, 0%, for immunotherapy and 4 of 22, 18%, for targeted therapy) (Menzies 2017). These data, while preliminary, further support our proposed study to combine the potential benefits of targeted therapy (rapid efficacy) with immunotherapy (durability) for BRAFm and immunotherapy for BRAFwt high-risk melanoma.

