### 1.9b Rationale for the proposed study

Combination therapy with BRAF and MEK inhibitors and immunotherapeutic agents for patients with BRAFV600 mutation-positive melanoma is supported by a strong scientific and clinical rationale based on 1) their complementary mechanisms of action, 2) observations that RAF and MEK inhibitors may enhance anti-tumor T cell-mediated immunity (Zhu 2016), and 3) the potential to deliver both the high response rate observed with BRAF and MEK inhibitors and the prolonged duration of response (DOR) that may be elicited with immune modulation. Coupled with the clinical data described above, several lines of nonclinical and biomarker evidence support this therapeutic strategy in BRAFV600 mutation-positive melanoma.

Nonclinical studies have indicated that BRAFV600 mutation-positive melanoma induces an immunosuppressive tumor microenvironment that can be reversed by BRAF and MAPK pathway inhibitors (Sumimoto 2006). In BRAFV600 mutation-positive melanoma cell lines, BRAF inhibitors and MEK inhibitors were shown to increase antigen expression and enhance reactivity to antigen-specific T lymphocytes (Boni 2010). MEK inhibition has also been shown to increase tumor major histocompatibility complex (MHC) expression and PD-L1 expression in triple-negative breast cancer cells in vivo and in vitro (Loi 2016).

In tumor biopsies from melanoma patients, BRAF and MEK inhibitors, alone or in combination, have been shown to increase melanoma antigen expression, MHC expression, T-cell infiltration, and PD-L1 expression (Wilmott 2012; Frederick 2013; Kavakand 2015; Liu 2015; Hu-Lieskovan 2015).

Additional MAPK inhibition effects may further modulate the tumor microenvironment in ways that could enable an improved immune reaction against the tumor. These effects include increased recruitment and activation status of CD8+ and CD4+ T cells, increased tumor antigen presentation, and reduced secretion of reduced granulocyte-colony stimulating factor with reduced mobilization and activity of CD11 + GRL + myeloid-derived suppressor cells (MDSCs) (Phan 2013; Liu 2015; Ebert 2016; Loi 2016), as well as reduced expression of angiogenesis factors with altered tumor vascular support (Ciuffreda 2009; Chang 2013; Mohan 2015).

Although the MAPK pathway is important for survival and function of immune cells, it has been shown that BRAF-targeted inhibition does not impair overall immune competency in cancer patients (Hong 2012).

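### Section 16.22 does not separate or stratify its pCR versus non-pCR biomarker comparisons by arm, so a combined comparison can show arm differences as apparent markers of response

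*Combined protocol and SAP*

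**What the plan says.** Section 16.22 sets out the molecular and microenvironment comparison of responders with non-responders "in patients with stage III melanoma after neoadjuvant vem/cobi/atezo or atezo, followed by surgery and adjuvant atezo". The methods are binomial intervals for a difference in proportions, or "t confidence intervals for the difference in two independent means", and their stated purpose is to "gain preliminary insights into the difference in these biomarkers among those who achieve a pCR and those who did not". For T cell receptor clonality, "A two sample Wilcoxon rank sum test will be used to assess whether the percent change" differs by pCR status, with a waterfall plot by pCR status and "a 95% binomial confidence interval for the difference in the parameter" between the two groups. Circulating tumour DNA is correlated with pCR and graphed by pCR status. None of these items mentions arm, cohort or BRAF status.

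Other sections do. In Section 16.21, for the RFS biomarker analysis, "stratified Cox modeling will be conducted with patient cohort as the strata". Sections 16.111 and 16.112 estimate pCR, PET/CT change and toxicity for each cohort, and Section 16.12 estimates RFS for each regimen.

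For Arm C, Section 16.22 says that the same correlative studies will be done as for Arms A and B. It does not say whether Arm C is analysed alone or together with them.

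**The concern.** Arm can confound a combined comparison if it is related both to pCR and to the marker. The protocol gives reason to expect both.

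- **Arm and pCR.** Section 1.42 cites a combined analysis of neoadjuvant trials: "They saw a pCR in 39% to immunotherapy and 55% to targeted therapy". Section 1.9c1 also says that pathologic response is lower with immunotherapy than with targeted therapy, and gives 13-50% for pCR or near-pCR with immunotherapy.
- **Arm and marker.** Section 1.9b says that BRAF and MEK inhibitors "have been shown to increase melanoma antigen expression, MHC expression, T-cell infiltration, and PD-L1 expression". The panel in Section 17.42 includes CD8 and CD4 T cells, PD-L1 and HLA class 1 and 2. Pretreatment markers cannot be moved by study drug, but Section 1.9b also links BRAF-mutant melanoma to an immunosuppressive microenvironment, and BRAF status defines Arms A and B (Section 5.1).

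A marker that reflects only which drugs a patient received could then be taken for a marker of response. The items affected are objective 2.33, the ctDNA-by-pCR comparison under objective 2.35, and the clonality-by-pCR test in Section 16.22.

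**Working it through.** Section 16.22 states no sample size, power or error rate, so there is no figure of the plan's own to reproduce.

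**Inputs**
- Arms A and B: 15 patients each (schema). Arm C: 32 patients (Section 16.1112).
- pCR: 55% for targeted therapy and 39% for immunotherapy (Section 1.42). The counts behind them agree: 22/40 = 55.0% and 7/18 = 38.9%.
- Wide-gap case: 58%, from a targeted-therapy trial in Section 1.42, against 13%, the low end of the range in Section 1.9c1, which includes near-pCR.
- Marker shift D, in within-arm SD units: not in the documents. Assumed to be 0 to 2 SD, in Arm A only.
- Two-sided 0.05 assumed for the t and Wilcoxon comparisons. Section 16.22 gives 95% only for the clonality proportions.

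**Formula.** For a marker unrelated to pCR within each arm, the expected spurious difference is D × (Arm A's share of the pCR group − Arm A's share of the non-pCR group).

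**Arms A + B, 55% vs 38.9%**
- Expected pCR: 15 × 0.55 = 8.25 in A and 15 × 0.389 = 5.83 in B. Arm A share = 8.25/14.08 = 0.586.
- Expected non-pCR: 6.75 in A and 9.17 in B. Arm A share = 6.75/15.92 = 0.424.
- Spurious difference = D × (0.586 − 0.424) = 0.16 D.

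**If Arm B's marker also moves.** Arm B receives cobimetinib, a MEK inhibitor (Section 7.12).
- Half the shift in B: (0.586 + 0.5 × 0.414) − (0.424 + 0.5 × 0.576) = 0.793 − 0.712 = 0.08 SD at D = 1.
- The same shift in B: zero for Arms A + B.

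**All three arms, 55/39/39%.** Arm A's shares are 0.311 and 0.190, giving 0.12 D. If B shifts equally, (0.311 + 0.220) − (0.190 + 0.258) = 0.08 D.

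**Wide gap, Arms A + B, 58% vs 13%.** Arm A's shares are 8.7/10.65 = 0.817 and 6.3/19.35 = 0.326, giving 0.49 D.

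**False-positive rates.** These come from a simulation of a null marker shifted in Arm A only, with 4,000 runs per setting. The Monte Carlo standard error at 5% is √(0.05 × 0.95/4000) = 0.3 percentage points.

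| Setting | D | t test | Wilcoxon |
|---|---|---|---|
| A+B, 55% vs 39% | 1 | 6.6% | 6.5% |
| A+B, 55% vs 39% | 2 | 11.3% | 10.8% |
| A+B, 58% vs 13% | 1 | 20.5% | 19.4% |
| A+B, 58% vs 13% | 2 | 47.3% | 47.4% |
| A+B, 47% in both (assumed) | 1 | 5.5% | 5.1% |
| A+B+C, 55/39/39% | 1 | 7.5% | 7.0% |
| A+B+C, 55/39/39% | 2 | 11.0% | 10.1% |

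With arm stratification (van Elteren test, or a linear model with an arm term) the rate stayed at about 4% to 6% in every setting.

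**The case against.** **Pooling is inferred.** No sentence says that the arms are combined. Section 1.9b speaks of finding response biomarkers in both cohorts, and the Arm C wording fits repeating the studies in Arm C alone. This stands in part. A combined analysis remains the natural reading for Arms A and B: Section 16.21 uses the same joint naming of regimens for an analysis that is plainly combined, and objective 2.33 joins all three regimens in one responder comparison. For Arm C the text is silent.

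**The pCR gap is uncertain.** It rests on 7/18 versus 22/40 (Fisher's exact p about 0.39), in patients given other regimens. The 13% counts near-pCR and comes from immunotherapy, whereas Arm B adds a MEK inhibitor. This stands, so the wide-gap results are a stress test, not a forecast.

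**The work is exploratory.** This lowers the stakes. It does not explain the omission, because Section 16.21 is also described as preliminary and is stratified.

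**Stratifying costs precision.** This stands. At 13% pCR, Arm B would have 15 × 0.13 = about 2 pCR patients.

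A reader might infer that arm differences are bound to appear as response markers in every comparison. The documents do not support that: bias needs both pCR and the marker to differ by arm. Section 1.9b concerns antigen expression, MHC, T-cell infiltration and PD-L1; it does not show that the drugs shift clonality or ctDNA independently of response.

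**Conclusion.** The point holds as a gap in the analysis text. As written, Section 16.22 allows a combined comparison that arm can confound, and the protocol's own rationale makes this plausible for the tumour immune markers.

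The expected size is modest. With a marker shift in Arm A only and the cited 55% versus 39%, the spurious difference for Arms A and B is about 0.16 SD per SD of shift, with t-test false positives of about 6.6% at 1 SD and 11.3% at 2 SD. The difference halves if Arm B's marker moves half as far, vanishes if pCR rates are equal, and becomes large only with a wide pCR gap. The shift is an assumption throughout.

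A reader might go further and say that the correlative objectives are defeated, including objective 2.36. That is not supported. Objective 2.36 compares receptor diversity and clonality between tissues and time points and contains no pCR comparison; the affected item is the clonality-by-pCR test in Section 16.22. No decision stated in the plan depends on these results.

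**What to change.** State in Section 16.22 that pCR versus non-pCR comparisons are shown by arm, and that any combined comparison is stratified by arm:

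- van Elteren test in place of the two-sample Wilcoxon test;
- arm-adjusted differences in means in place of the two-sample t intervals;
- Mantel-Haenszel risk differences in place of the unstratified binomial differences;
- arm labels on the waterfall plot and graphs.

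Add BRAF status as a further factor within Arm C, where 19 wild-type and 13 mutated patients are planned (Section 16.112); arm alone does not control for it there. Say whether Arm C is combined with Arms A and B. In the same edit, reconcile the regimen names: Sections 16.21 and 16.22 give the second regimen as atezolizumab, while objective 2.112 gives cobimetinib/atezolizumab.

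The change is to wording only and needs no new patients, samples or assays. The cost is wider intervals, and within-arm estimates will be imprecise with 15 patients in each of Arms A and B.

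### Section 16.22: the added proportion of patients whose T-cell clonality changed has no direction or size, so the only interval planned for clonality by pCR says almost nothing if read literally

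*Combined protocol and SAP*

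**What the plan says.** Section 16.22 (Other correlative evaluations) plans the clonality analysis by pathologic response in this order.

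- For intra-tumoral and peripheral blood T cells, "the percent change in the clonality after post neoadjuvant therapy from pre-neoadjuvant therapy levels will be determined".
- Each patient's change is then drawn as a waterfall plot, split by response group.
- "A two sample Wilcoxon rank sum test will be used to assess whether the percent change in intra-tumoral T cells from the primary lesion" differs by pCR status; blood is tested in the same way.
- An additional summary follows: "Also, the proportion of patients who have a change in intra-tumoral T cell clonality", and the same for blood, where "the proportion of patients who have a change in peripheral blood T cell clonality will be determined".
- For each of these two proportions the plan calls for "a 95% binomial confidence interval for the difference in the parameter between those who have a pCR and those who do not".

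Neither 16.22, nor the assay descriptions in 14.45 and 17.44, nor objective 2.36 gives a threshold, a sign or an assay-repeatability limit for calling a patient changed. The confidence intervals mentioned earlier in 16.22 belong to the tissue and RNA-Seq biomarkers. For clonality by pCR, the interval on the two proportions is the only one planned.

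**The concern.** The same paragraph handles clonality as a number on a continuous scale and takes its percent change. Two samples from one patient will almost never give exactly the same value. If any difference counts, the proportion is close to 100% in both response groups and its difference is close to zero by construction.

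The missing direction matters separately. If clonality rose in responders and fell in non-responders, an unsigned rule would count both as changed and the contrast would disappear, even with a size threshold added.

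What is at stake is the one interval estimate in this part of the plan. In a pilot, an effect size with its uncertainty is more use for later work than a p-value, and the Wilcoxon test is specified without one. If size and direction are instead settled once pCR status is known, groups this small leave room for the choice to shape the result.

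**Working it through.** **Plan's own figure.** There is none to reproduce. The documents give no expected proportion, cut-off, power or sample size for this analysis.

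**Inputs from the documents.** There are 15 patients in each of Arms A and B (16.1111) and 32 in Arm C (16.1112). Section 1.9c1 cites complete or near-complete response rates of 13-50% for neoadjuvant immunotherapy.

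**Assumed inputs.** The pCR/non-pCR splits are 10/22 and 16/16 for 32 patients, and 7/8 and 5/10 for 15. The assumed spread of change and effect sizes are stated where used.

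**Step 1: how many patients count as changed?** Suppose within-patient change is normal with SD 0.05 clonality units and values are reported to three decimals. With no mean shift, the chance of a recorded change of exactly zero is about 0.001 × 0.399 / 0.05 = 0.008. About 99% of patients then count as changed. Simulation gave 99.2-99.4% in every scenario, with or without a true effect.

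**Step 2: the interval when everyone counts.** The plan does not name the method, so the Newcombe interval, built from Wilson limits, is used. When all n patients count, the Wilson lower limit is n/(n + z²) and the upper limit is 1, with z² = 3.84. The interval for the difference is then

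-z²/(n₁ + z²) to +z²/(n₂ + z²),

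where n₁ is the pCR group. For 10/22 this is -3.84/13.84 = -0.278 to +3.84/25.84 = +0.149. Only group sizes enter, so clonality data cannot move it.

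| pCR / non-pCR | All counted, 95% interval (points) | One non-pCR patient unchanged |
|---|---|---|
| 16 / 16 | -19.4 to +19.4 | -13.8 to +28.3 |
| 10 / 22 | -27.8 to +14.9 | -23.5 to +21.8 |
| 7 / 8 | -35.4 to +32.4 | -24.4 to +47.1 |
| 5 / 10 | -43.4 to +27.8 | -34.2 to +40.4 |

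At the low end of the cited response range, 0.13 × 32 is about 4. A 4/28 split gives -3.84/7.84 = -49 to +3.84/31.84 = +12 points.

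**Step 3: the same data analysed other ways.** In 3,000 simulated trials per split, percent change was normal and the pCR group was shifted up by 1 SD. The table shows how often each analysis found the difference: p < 0.05 for Wilcoxon, 95% interval excluding zero for the proportions.

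| Split | Wilcoxon (planned) | Proportion with an increase | Any non-zero change |
|---|---|---|---|
| 16 / 16 | 74% | 52% | 0% |
| 10 / 22 | 67% | 44% | 0% |
| 7 / 8 | 38% | 27% | 0% |

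**Step 4: is a size threshold enough?** Take an unsigned rule, absolute change above 1 SD. For a 1-SD shift, the interval excluded zero in 21-23% of runs at 10/22 and 16/16. For opposite shifts of +0.5 and -0.5 SD, each group has the same chance of counting: P(Z > 0.5) + P(Z < -1.5) = 0.309 + 0.067 = 0.375. The true difference is exactly zero, and the interval excluded zero in only about 4-5% of runs. The signed proportion excluded zero in 59-61% of runs for those opposite shifts. Direction is needed as well as size.

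**The case against.** The strongest reply is that the proportion is an afterthought. The plan first computes percent change, displays it by pCR status and tests it with a Wilcoxon test, all of which use sign and relative size. A reader might infer that the trial cannot separate pCR from non-pCR on clonality. The documents do not support that: under the assumptions above, the planned Wilcoxon test finds a 1-SD shift in 67-74% of Arm C-sized trials. Nor is the trial left with nothing to look at, since the waterfall plot shows each patient's change by group.

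A reader might also infer that the plan prescribes an any-non-zero rule. It does not; that is the literal reading of an undefined term. A signed definition would make the same interval usable, so the binomial interval as a method is not at fault. A table showing about 100% against about 100% would also expose the problem at once, which limits the risk of its being taken as evidence of no difference.

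These replies narrow the point without removing it. The criterion is undefined everywhere, the literal reading is uninformative, and a threshold without a sign loses opposite changes. The paragraph still offers no formal effect estimate beside the Wilcoxon test.

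**Conclusion.** The point holds for the supplementary proportion and its interval only. Taken literally, that interval is fixed by group sizes and says almost nothing about clonality and response. The percent-change analyses planned before it stand.

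The Step 2 intervals follow exactly from the literal reading, the Newcombe method and the stated splits. The power figures rest on assumed normal changes, effect sizes and pCR splits that the documents do not give; the 99% figure also rests on the assumed SD and reporting precision. They illustrate the contrast between analyses and do not predict this trial's power. Whether arms are analysed separately or pooled is not stated; pooling would narrow the interval without making it informative.

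Severity is minor. This is one summary within an exploratory correlative analysis, and no primary endpoint, safety rule or treatment depends on it. It is worth correcting because the better estimator uses data the plan already computes.

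**What to change.** In 16.22, replace the two changed/unchanged proportions and their binomial intervals with the Hodges-Lehmann estimate of the pCR minus non-pCR difference in signed percent change in clonality, with its 95% confidence interval. This is the median of all between-group pairwise differences (10 × 22 = 220 of them for a 10/22 split), and its interval comes from inverting the rank-sum test, so it matches the Wilcoxon test already planned. Report it beside that test.

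Do this for peripheral blood, where the table in 14.1 schedules samples before treatment and at the end of neoadjuvant treatment, and for tissue where paired samples exist. The table in 17.1 lists T-cell receptor tissue only at surgery.

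If a proportion is kept, define it in advance as the proportion of patients with an increase and keep the interval for the difference in that proportion.

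The cost is one or two sentences in 16.22. No new samples, assays or patients are needed.
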